**Combined Bleaching Technique: Efficacy and Tooth Sensitivity - A Randomized,
Double Blind Clinical Trial**

ClinicalTrials.gov ID: NCT03089216

May 1, 2018

Objective

This study evaluated the efficacy, color stabilization, and tooth sensitivity (TS) during and after the use of a combined bleaching technique, varying the application time of 35% hydrogen peroxide (HP) and the use of a desensitizing dentifrice containing arginine (ARG).

Study design

This is a randomized controlled clinical trial, parallel and double blinded, with a similar allocation rate between groups, registered at clinicaltrials.gov under the identification number NCT03089216. The study has been conducting at the School of Dentistry of the Federal University of Goias (UFG), following CONSORT statement, after the approval of the Ethics Committee of the Federal University of Goias, Brazil (CAAE: 52047115.2.0000.5083).

One hundred and eight participants were randomly assigned to 4 groups ($n = 27$): OFF40 (without ARG): two 20-minute HP applications (2x20); D-OFF40 (with ARG): two 20-minute applications (2x20); OFF20 (without ARG): one 20-minute HP application (1x20); and D-OFF20 (with ARG): one 20-minute HP application (1x20). In all groups, at-home bleaching was performed with 10% carbamide peroxide (CP) for two hours daily for 16 days. Color evaluations were performed before bleaching and at 5, 8, 12, and 16 days from the beginning of the procedure, and 7 and 30 days after the end of the treatment, with VITA Classical and VITA Bleachedguide 3D-MASTER shade guides (Δ SGU) and a digital spectrophotometer, VITA Easyshade (VITA Zahnfabrik). The TS evaluation was performed with a visual analogue scale (0-10) and numerical scale (0-4) in different periods.

Statistical Analysis Plan

Statistical analyses will be performed using SPSS 20.0 (SPSS Inc., Chicago, IL, USA) with $\alpha = 0.05$. The means of the SGU at baseline and after different assessments will be calculated for each group. In order to evaluate whether the bleaching therapies were effective or not, the data from the SGUs will be analyzed using the Kruskal-Wallis and Mann-Whitney tests for between-group comparisons,

and the Friedman and Wilcoxon tests with Bonferroni correction ($\alpha = 0.002$) for within-group comparisons. The ΔE values will be submitted to two-way analysis of variance (ANOVA).

The Tooth Sensitivity intensity will be analyzed using Kruskal- among-group comparisons within each evaluation time (baseline, immediately after the in-office bleaching, daily during the at-home bleaching, and up to 48 hours after the treatment). The comparisons among the assessment times within each group will be performed using the Friedman and Wilcoxon tests with Bonferroni correction ($\alpha = 0.008$).

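### The between-group SGU tests leave out the pre-bleaching SGU already collected; the tests are valid, but adjusting for it is a near-free gain in power of unknown size

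*Combined protocol and SAP*

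**What the plan says.** The Study design section gives the timing of color assessment: "Color evaluations were performed before bleaching and at 5, 8, 12, and 16 days from the beginning of the procedure". Two further readings follow once treatment has ended, at 7 and at 30 days. That is one pre-bleaching reading and six later ones. The instruments are introduced as "with VITA Classical and VITA Bleachedguide 3D-MASTER shade guides (Δ SGU"), so the label there is a difference.

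The Statistical Analysis Plan uses different wording: "The means of the SGU at baseline and after different assessments will be calculated for each group". For inference it says that "the data from the SGUs will be analyzed using the Kruskal-Wallis and Mann-Whitney tests for between-group comparisons", and the same sentence continues "and the Friedman and Wilcoxon tests with Bonferroni correction ($\alpha = 0.002$) for within-group comparisons". The overall level is 0.05. The two-way ANOVA is reserved for ΔE: "The ΔE values will be submitted to two-way analysis of variance (ANOVA").

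No ANCOVA, rank ANCOVA or other adjustment of SGU for its pre-bleaching value appears anywhere. The plan also does not say outright whether the between-group tests are run on SGU or on its change from baseline.

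**The concern.** Each participant is due a shade reading before treatment. If starting shade predicts later shade, part of the spread in the outcome is explained by a value the trial already holds, and a test that ignores it leaves that spread in the error. A change score uses the baseline, but with a fixed weight of one, which adds noise when the correlation is low.

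Groups are small (27 each), and no stratification on shade is described. Chance differences in starting shade therefore carry into a raw comparison in proportion to the baseline-outcome correlation. What is at stake is the power of the between-group color comparisons, not their type I error.

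**Working it through.** **Inputs from the documents.** 108 participants, 4 × 27 = 108; seven color times (1 + 4 + 2); alpha 0.05 overall and 0.002 for within-group SGU comparisons. **Assumptions, because the documents give none:** rho from 0 to 0.7, equal SDs before and after, a 16-step scale, and the effect sizes below. No effect size, SD or power is stated, so the sample size cannot be reproduced.

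**1. Which variable is tested?** Seven times including baseline give 7 × 6/2 = 21 pairs, and 0.05/21 = 0.00238, which prints as 0.002. Six change scores give 6 × 5/2 = 15 pairs, and 0.05/15 = 0.0033, which does not. The within-group tests therefore fit raw SGU, and one sentence sends the same SGU data to the between-group tests. This makes raw SGU likelier but does not settle it.

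**2. Chance imbalance.** The SE of a pairwise baseline difference is √(2/27) = 0.272 SD. A one-SE imbalance shifts a raw comparison by rho × 0.272 SD: 0.08 SD at rho 0.3, 0.14 at 0.5 and 0.19 at 0.7.

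**3. Normal-theory precision.** The relative variance of a between-group contrast is 1 for raw SGU, 2(1 − rho) for change and 1 − rho² for baseline-adjusted SGU. So 27 adjusted per group are worth 27/(1 − rho²) raw, or 27 × 2(1 − rho)/(1 − rho²) change scores:

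| rho | 0 | 0.1 | 0.2 | 0.3 | 0.5 | 0.7 |
|---|---|---|---|---|---|---|
| against raw | 27.0 | 27.3 | 28.1 | 29.7 | 36.0 | 52.9 |
| against change | 54.0 | 49.1 | 45.0 | 41.5 | 36.0 | 31.8 |

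**4. Correction for ranks.** SGU is a stepped score and the natural method is rank-based. With scores rounded and clipped to 1–16 (SD 3 steps), a latent rho of 0.7 gives an observed Spearman correlation of about 0.675 mid-scale and about 0.62 when post-bleaching values pile up at the end step. Then 27/(1 − 0.675²) = 49.6 and 27/(1 − 0.62²) = 43.9. For the rank method, 44 to 50 is the fair figure, not 53.

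**5. Simulated power (%), four groups of 27, one group shifted 0.8 SD.** Raw and Quade rows use 10,000 runs per cell; change rows use 4,000.

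| rho | 0 | 0.3 | 0.5 | 0.7 |
|---|---|---|---|---|
| Mid-scale: Kruskal-Wallis, raw | 83.0 | 83.1 | 83.2 | 82.3 |
| Mid-scale: Kruskal-Wallis, change | 50 | 66 | 81 | 97 |
| Mid-scale: Quade | 83.2 | 86.5 | 91.9 | 98.2 |
| End-step pile-up: Kruskal-Wallis, raw | 79.1 | 79.6 | 79.7 | 80.2 |
| End-step pile-up: Kruskal-Wallis, change | 33 | 46 | 57 | 76 |
| End-step pile-up: Quade | 79.3 | 82.5 | 88.4 | 96.2 |

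In the raw and Quade pile-up rows about 43% of post-bleaching values sit at the end step. At rho 0.1 and 0.2 the mid-scale pairs are 82.7 against 83.0 and 82.5 against 84.0, so the gain there is negligible. Under the null, rejection in the 10,000-run cells was 4.4–5.0% for raw Kruskal-Wallis and 4.4–5.5% for Quade. Quade was never below raw or change scores.

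**The case against.** The strongest reply is that a valid analysis needs no repair, and that the size of the benefit rests on a correlation found nowhere in the documents. At rho 0.3 the gain over raw SGU is only about three points of power. This stands as a limit on what can be claimed: the point is an improvement worth making, and its benefit may turn out small.

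A second reply is that the 0.002 level belongs to the within-group tests. A plan could test raw SGU within groups and Δ SGU between them, and other divisors also print as 0.002 (0.05/28 = 0.0018). This stands too. It reverses the pattern of the gain by rho, but it does not remove the gain, since adjustment does at least as well against either variable.

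A third reply is that the change is late: assignment and color evaluation are in the past tense, and nothing shows whether the blind is intact. This is a reason to date the change, make it before any unblinded analysis and keep the planned tests in the report. Quade's method also yields a test and not an adjusted difference with an interval, so the gain is in power.

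A reader might go further and infer that the unadjusted comparison is biased or invalid. It is not: randomization protects its type I error, and the simulations agree. A reader might also infer that adjustment calls for one main guide and one main time. The power argument does not support that. The Objective includes color stabilization, which an end-of-bleaching reading alone could not show.

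**Conclusion.** The point holds as a recommended improvement, with medium confidence. The between-group SGU tests make no covariate use of the pre-bleaching SGU, and adjusting for it costs almost nothing.

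- **If raw SGU is tested (likelier):** the gain is nil at rho 0, negligible up to about 0.2, and substantial from 0.5. At 0.7, 27 per group are worth about 44 to 50 with ranks.
- **If Δ SGU is tested:** the gain is largest at rho 0 and smallest at 0.7 (54 down to 32 equivalents under normal theory).

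These sizes depend on the assumed correlations, equal SDs, scale and shifts. Validity here means type I error per test; multiplicity across the pairwise tests is a separate question. Nothing is claimed for ΔE, where the documents allow no calculation.

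**What to change.** In a dated SAP change made before any unblinded analysis, name the analysed variable and add the covariate. Suggested text:

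> Each planned between-group SGU comparison (each guide, each post-baseline time) tests SGU adjusted for pre-bleaching SGU on the same guide by Quade rank ANCOVA across the four groups: rank outcome and baseline over all participants, regress outcome ranks on baseline ranks, and compare the residuals by one-way ANOVA. Pairwise follow-ups use the same residuals. Unadjusted Kruskal-Wallis and Mann-Whitney tests are reported as a sensitivity analysis. Δ SGU is a descriptive summary.

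Naming a single main guide and time is a separate, optional decision and is not part of this change.

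The cost is SAP text only, with no new data or participants. The method needs only ranking, a regression and a one-way ANOVA. The downside is one degree of freedom and a late change that must be dated. If an unblinded analysis has already been run, the adjusted test should be reported as an addition and labelled post hoc.

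### Colour stabilization is a named objective, but the SAP plans no interval for the change after treatment, and a non-significant test at 0.002 cannot show that colour was stable

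*Combined protocol and SAP*

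**What the plan says.** The Objective section sets three targets: "This study evaluated the efficacy, color stabilization, and tooth sensitivity (TS) during and after the use of a combined bleaching technique". It also names what is varied: "varying the application time of 35% hydrogen peroxide (HP) and the use of a desensitizing dentifrice containing arginine (ARG").

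Under Study design, 108 participants are in four groups of 27. At-home bleaching lasts 16 days. Colour is assessed at baseline, on days 5, 8, 12 and 16, "and 7 and 30 days after the end of the treatment". The instruments are listed as "with VITA Classical and VITA Bleachedguide 3D-MASTER shade guides (Δ SGU) and a digital spectrophotometer".

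The Statistical Analysis Plan gives the SGU tests one purpose: "In order to evaluate whether the bleaching therapies were effective or not, the data from the SGUs will be analyzed". It plans:

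- SGU means per group at each assessment;
- between-group tests, "using the Kruskal-Wallis and Mann-Whitney tests for between-group comparisons";
- within-group tests, "and the Friedman and Wilcoxon tests with Bonferroni correction ($\alpha = 0.002$) for within-group comparisons";
- a two-way ANOVA of ΔE, with neither factors nor reference visit named.

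The SAP does not mention stabilization, relapse or rebound. It plans no confidence interval for any outcome.

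**The concern.** Efficacy and stabilization ask opposite things of a test. For efficacy the hoped-for result is a change from baseline, and a strict significance level guards against claiming it wrongly. For stabilization the hoped-for result is no change after day 16, and a strict level makes that result easier to obtain by lack of power alone. The SAP does not say how a non-significant day 16 versus follow-up comparison will be read. If it were read as stable colour, a moderate rebound could pass unnoticed.

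There is also a between-group side. The trial varies application time and dentifrice, so whether either affects the change after treatment is part of the question. The planned between-group tests are not said to apply to that change, and they may be meant only for comparing groups at each visit.

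**Working it through.** **Inputs.** From Study design: n = 27 per group, four groups, seven colour visits. From the SAP: α = 0.05 overall and 0.002 within groups. Not in the documents: the SD of the change, the expected rebound, dropout and sidedness. I assume two-sided tests and complete data, and express changes in SDs of the paired change.

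**1. The plan's own threshold.** Seven visits give 7 × 6 / 2 = 21 pairs, and 0.05 / 21 = 0.00238, which rounds to the stated 0.002. So 0.002 is not an error. Day 16 versus +7 days and day 16 versus +30 days are presumably two of the 21 pairs. The count is not stated; 28 pairs (eight visits) would also round to 0.002, but the document lists seven visits.

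**2. What can be recovered from planned output.** With complete data, the mean change from day 16 to follow-up is the difference of two planned visit means. Its standard error needs the SD of the paired differences, which visit means do not give.

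**3. Power of the within-group test.** A paired t-test is used as a stand-in, with noncentrality d√27 on 26 df. For d = 0.5 the noncentrality is 0.5 × 5.196 = 2.598.

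| Level | Critical t(26) | Power, d = 0.5 | d for 80% power |
|---|---|---|---|
| 0.002 | 3.435 | 0.234 | 0.83 |
| 0.05 | 2.056 | 0.706 | 0.56 |

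The Wilcoxon test on simulated normal changes at 0.002 gives 0.18 (asymptotic p) to 0.22 (exact p). The range is therefore about 18–23% for continuous changes. Rounding changes to whole shade units lowers it to about 13–16%. A rebound of 1.0 SD would be detected with about 91–95% power.

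A true 0.5 SD rebound would thus be non-significant at 0.002 roughly four times in five. Even at 0.05 it would be missed about 1 − 0.71 = 29% of the time, so relaxing the level does not turn non-significance into evidence of stability.

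**4. What an interval would deliver.** 95% half-widths in SDs of the change:

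- within one group: t(26) / √27 = 2.056 / 5.196 = 0.40;
- one factor level against the other, 54 v 54 on 104 df: 1.983 × √(2/54) = 1.983 × 0.1925 = 0.38.

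If the SD were 1, 2 or 3 shade units (assumed), the within-group half-widths would be 0.40, 0.79 and 1.19 units.

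**The case against.** The strongest reply is that the contrast is probably tested already, that its point estimate follows from the planned means, and that nowhere does the SAP say p > 0.002 will be taken as stability. All of this stands. A reader might infer that stabilization goes unanalysed, or that no estimate of the change will be available. The documents support neither. What is missing is a designated change, its precision, and a stated between-group comparison of it.

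A second tempting argument sets the 0.002 test beside a 95% interval and notes how often they disagree. For a 0.5 SD rebound, the test is non-significant while the 95% interval excludes zero in about 52% of simulated groups. That mostly reflects two different error levels. With a matched 99.8% interval the disagreement falls to 5.7%, and with both at 0.05 to 3.9%. It should not be used against the plan. The case rests on the asymmetry between failing to find change and showing stability.

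Three further points also stand:

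- Stabilization is not defined. The +7 versus +30 days comparison, or a plateau over days 5 to 16, are possible readings, so choosing day 16 to follow-up is a judgement.
- ΔE is not defined. If it is a distance between visits it cannot be negative, and an interval for it cannot be read against zero.
- The document describes randomization and colour assessments in the past tense, so prespecification may no longer be possible.

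**Conclusion.** The point holds as a cheap improvement, not as an error in the plan. The SAP does not tie any analysis to the stabilization objective, plans no interval for the change after treatment, and states no between-group comparison of that change. A non-significant within-group test at 0.002 with 27 participants cannot support stability, because power for a 0.5 SD rebound is about 18–23%; non-significance at 0.05 would not establish it either.

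These figures rest on complete data, two-sided tests, roughly normal changes and a rebound size chosen for illustration. The gap itself depends on none of them. Whether the ΔE ANOVA covers the post-treatment change cannot be determined from the text.

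**What to change.** Add a short paragraph to the SAP:

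- Name the SGU change from day 16 to 30 days after treatment as the main stabilization estimate, with the change to 7 days as supportive, for each shade guide.
- Report it with a 95% CI within each group and for the two factor contrasts (application time, dentifrice; 54 v 54). Choose a mean with t-interval or a Hodges-Lehmann interval in advance. With one-unit tied changes the t-interval covers about 92–96%, so call it approximate.
- Label these intervals as estimates not adjusted for multiplicity.
- Base any stability statement on the intervals, not on p > 0.002. If a limit of acceptable change is used, fix and date it before unblinded colour data are examined. Without one, report the intervals and make no formal stability claim.
- For the spectrophotometer, state the reference visit. If ΔE is a non-negative distance, do not read its interval against zero; compare groups, or use the change in a signed colour measure.
- Leave the planned tests as they are. If colour data have already been examined, date the addition and label it post hoc.

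The cost is a few sentences and a small table, with no new data, visits or participants. The downside is that stability becomes harder to claim. If the true change is zero and a limit of 0.5 SD were used (purely for illustration), the within-group 95% CI would lie inside it about 42% of the time; at 0.75 SD, about 93%.

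### Free improvement: Holm's step-down rule could replace single-step Bonferroni for the within-group visit comparisons at the same 5% family-wise error, once the tooth-sensitivity family is defined

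*Combined protocol and SAP*

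**What the plan says.** The Statistical Analysis Plan sets an overall alpha of 0.05. For shade guide units (SGU) its within-group wording is "and the Friedman and Wilcoxon tests with Bonferroni correction", and the threshold attached to it is 0.002. The Study design section gives the reading times: "Color evaluations were performed before bleaching and at 5, 8, 12, and 16 days from the beginning of the procedure". Two more readings follow once treatment has ended, at 7 and at 30 days. For TS intensity, comparisons among times within each group "will be performed using the Friedman and Wilcoxon tests with Bonferroni correction", with alpha given as 0.008. The TS times are listed as "baseline, immediately after the in-office bleaching, daily during the at-home bleaching, and up to 48 hours after the treatment", and at-home bleaching lasts 16 days.

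No stepwise procedure is mentioned, and the number of comparisons in each family is not stated. No simultaneous confidence intervals are planned. The documents give no SD, effect size or power for these comparisons. The Objective section lists colour stabilization, and sensitivity during and after bleaching, among the aims.

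**The concern.** Single-step Bonferroni holds every pair of visits to the same threshold, however many other pairs are clearly different. In a bleaching trial, many shade pairs (baseline against each later reading) should reject easily. Single-step Bonferroni gives no credit for those rejections; Holm does.

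The pairs that could benefit are the subtler ones. Examples are the end of treatment against 7 or 30 days later, which is where loss of colour would show, and baseline against the last TS reading. These bear on the stated aims of colour stabilization and sensitivity after treatment. In both, a real change that is missed looks like a favourable result, so power that is available without extra error is worth taking.

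**Working it through.** **1. Reproducing the plan's thresholds.** Bonferroni: alpha / m, with m = k(k − 1)/2 pairs from k times.

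- Shade: baseline, days 5, 8, 12 and 16, and 7 and 30 days after treatment give k = 7. m = 7 × 6/2 = 21, and 0.05/21 = 0.00238, stated as 0.002. The family bound actually used is 21 × 0.002 = 0.042.
- TS: 0.008 matches k = 4, m = 4 × 3/2 = 6, and 0.05/6 = 0.00833. The bound used is 6 × 0.008 = 0.048.

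**2. Is k = 4 right for TS?** Only if the daily at-home scores become one value. If each of the 16 days counts, k is about 1 + 1 + 16 + 1 = 19 and m = 19 × 18/2 = 171. Bonferroni would then be 0.05/171 = 0.00029. The bound at 0.008 would be 171 × 0.008 = 1.37, which guarantees nothing.

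**3. Holm's thresholds.** Order the p-values and compare the i-th smallest with 0.05/(m − i + 1), stopping at the first failure. For shade the sequence runs 0.05/21, 0.05/20, … up to 0.05. If only the six baseline pairs reject, the next threshold is 0.05/15 = 0.0033, against 0.002 in the plan. That step needs no assumed SD.

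**4. Power on an SGU scale (assumed values).** n = 27, integer readings, between-person SD 1.5, within-person SD 1.0. In the changing profile, means are 9, 6.5, 5.5, 4.5 and 4.0 up to day 16, then rebound. In the flat profile, colour is constant from day 5 until rebound. Power for day 16 against 30 days after treatment:

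| Rebound | Profile | At 0.002 | Holm | Gain (points) |
|---|---|---|---|---|
| 0.5 SGU | changing | 4% | 11% | 7 |
| 0.75 SGU | changing | 20% | 36% | 16 |
| 0.75 SGU | flat | 18% | 26% | 8 |
| 1.0 SGU | changing | 44% | 67% | 23 |
| 1.0 SGU | flat | 47% | 59% | 12 |
| 1.5 SGU | changing | 90% | 97% | 7 |

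**5. Power on a standardized scale (assumed values).** n = 27, 3,000 runs, Wilcoxon tests, unit SD and within-person correlation 0.5. The SD of a difference is √(2 × (1 − 0.5)) = 1, so d is the mean difference in SD units. Target pair: day 16 against 30 days after (shade), or baseline against the last time (TS, k = 4).

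| Scenario | d | Plan's threshold | Unrounded Bonferroni | Holm |
|---|---|---|---|---|
| Shade, changing | 0.5 | 19.7% | 21.9% | 33.5% |
| | 0.7 | 49.9% | 52.5% | 67.0% |
| | 0.8 | 66.5% | 69.2% | 80.9% |
| Shade, flat before rebound | 0.5 | 18.0% | 19.6% | 24.5% |
| | 0.7 | 48.9% | 51.7% | 60.1% |
| | 0.8 | 70.5% | 72.6% | 78.9% |
| TS, other times also differ | 0.5 | 35.4% | 36.6% | 57.9% |
| | 0.7 | 72.5% | 73.8% | 86.8% |
| | 0.8 | 85.3% | 86.0% | 93.5% |
| TS, last time the only effect | 0.5 | 37.8% | 38.8% | 41.1% |
| | 0.7 | 72.5% | 73.7% | 77.2% |
| | 0.8 | 85.3% | 86.0% | 88.7% |

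The smallest shade gain is 24.5 − 18.0 = 6.5 points. TS gains run from 41.1 − 37.8 = 3.3 to 57.9 − 35.4 = 22.5 points. The step from the plan's threshold to unrounded Bonferroni is the part due to rounding down. Here it is 0.7 to 2.8 points, and about 1 to 4 for shade across all the runs.

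**6. Error control.** With no true differences, Holm and unrounded Bonferroni each made at least one false rejection in 2.6% of runs (21 pairs) and 4.2% (6 pairs). The chance of at least one rejection was identical for the two in every scenario, as theory requires.

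**The case against.** The strongest reply is that nothing here is wrong. Bonferroni is valid, simple to apply, and has matching simultaneous confidence intervals, which Holm lacks in simple form. That stands, although the plan reports no such intervals.

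Second, the Statistical Analysis Plan introduces the SGU tests as a way to judge whether bleaching worked. For that purpose no power is lost: in the changing shade profile, all six baseline pairs were rejected in every run at 0.002. No passage names day 16 against a later reading, or baseline against the last TS score, as a target pair. This also stands. The link to those pairs comes from the Objective section, where stabilization and sensitivity after bleaching are aims.

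Third, the size is assumed, and the profile with colour changing at every visit favours Holm. Hence the flat profile above, where the gain is roughly half as large. When the last TS time is the only effect, it is 3 to 5 points.

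A reader might infer more than the documents support:

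- *That the Bonferroni thresholds are an error, or that power is given up for nothing.* They reproduce correctly and protect the families they imply.
- *That Holm is always more powerful.* It is never less powerful, but gains only when another pair is already rejected.
- *That the subtle pairs face a harsher level than the others.* Under single-step Bonferroni every pair faces the same level.
- *That the plan will read non-significance as stability or as resolution of sensitivity.* No passage says so. If that reading were made, Holm would not cure it: at a 0.75 SGU rebound, Holm still misses 64% (100 − 36) in the changing profile.

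**Conclusion.** This is an optional efficiency gain, not a defect. The methodological part is certain: the same 5% family-wise error under any dependence, every Bonferroni rejection retained, and more rejections when other pairs have already been rejected.

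The size is not certain. It rests on assumed means, SDs and correlation, complete data for 27 per group, and for TS a family of 6 pairs. On those terms the gain for a single pair is about 6 to 23 points for shade and about 3 to 22 for TS, including the small part due to rounding.

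The TS part is conditional. The 6-pair family is inferred from 0.008, while the text lists daily at-home scores, and protection at 5% can be claimed only once the family is stated. Only within-group time contrasts are affected. The randomized comparisons of application time and dentifrice are untouched.

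**What to change.** In both places, replace the Bonferroni phrase and its fixed alpha with: *Holm step-down adjustment, family-wise alpha 0.05, over all visit pairs within a group*. State the number of pairs in each family and report Holm-adjusted p-values. With ordered p-values p(1) ≤ … ≤ p(m), the adjusted value for the i-th is the largest of min(1, (m − j + 1) × p(j)) over j ≤ i. This also removes the rounding of 0.00238 and 0.00833.

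For TS, first say how the daily at-home scores enter: as one defined summary value (6 pairs) or as separate days (about 171 pairs). Then apply Holm to that number.

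The cost is one phrase in two places, a sentence on the TS family, and a spreadsheet step on the Wilcoxon p-values from SPSS. Design and data collection do not change. The one small loss is that simple matching simultaneous intervals are no longer available. The change should be made before the comparisons are run; if they have already been run, it should be reported as a later change. Add a sentence that a non-significant pair is not evidence that colour is stable or that sensitivity has resolved.

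### The between-arm tooth sensitivity analysis gives separate tests at each time and no pre-specified overall answer for the 16-day at-home phase

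*Combined protocol and SAP*

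**What the plan says.** The Objective section sets out to evaluate "tooth sensitivity (TS) during and after the use of a combined bleaching technique". The two factors are how long the peroxide is applied and whether an arginine dentifrice is used. Under Study design, "One hundred and eight participants were randomly assigned to 4 groups" of 27, and at-home bleaching is done "for two hours daily for 16 days". On measurement, the same section says: "The TS evaluation was performed with a visual analogue scale (0-10) and numerical scale (0-4) in different periods".

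For TS intensity, the Statistical Analysis Plan specifies "among-group comparisons within each evaluation time (baseline, immediately after the in-office bleaching, daily during the at-home bleaching". The list of times closes with a 48-hour post-treatment period. The name of the test is cut off after Kruskal-. I treat that as a loss in reading the PDF and take Kruskal-Wallis to be meant. The only TS analysis across times is Friedman and Wilcoxon within each group, at a Bonferroni alpha of 0.008, and it does not compare arms. The two-way ANOVA is assigned to ΔE only. The overall level is 0.05. No correction across times is stated for the between-arm TS tests. The plan also names no per-participant TS summary, no main TS time and no main TS scale.

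**The concern.** The natural at-home question is whether arginine, or the shorter peroxide time, changes the TS a participant has over the 16 days. Taken as written, the plan answers it with 16 separate four-group tests. Each test uses one day's scores, in which everyone without TS that day ties at zero, and no test combines days.

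Two problems follow. If the daily tests are left uncorrected, a scattered significant day is likely whether or not there is an effect, so it cannot be interpreted. If they are corrected, most of the power is lost.

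If the daily scores are instead meant to be reduced to one at-home value, the plan does not say how. Mean, maximum or sum could then be chosen after the results are known.

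**Working it through.** **1. The plan's own threshold.** Bonferroni over all pairs of k times is 0.05 / [k(k−1)/2].
- TS: k = 4 gives 0.05/6 = 0.0083, printed as 0.008. The figure is reproduced.
- Color, as a cross-check: the seven visits in Study design (baseline; days 5, 8, 12 and 16; 7 and 30 days after) give 0.05/21 = 0.0024, printed as 0.002. The same rule was evidently used.
- TS with each at-home day counted: baseline + in-office + 16 days + 1 or 2 post-treatment scores is 19 or 20 times. That is 171 or 190 pairs, and an alpha of 0.00029 or 0.00026.

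So 0.008 fits four times, while the wording of the between-arm tests says daily. The two do not agree, and no collapsing rule connects them.

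**2. False positives from uncorrected tests.** For m independent tests at 0.05, the chance of at least one p < 0.05 is 1 − 0.95^m.
- m = 4: 18.5%
- m = 16: 56%
- m = 19: 62%

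Neighboring days are correlated and ties are heavy, so simulation is needed for a realistic figure.

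**3. Simulation of the at-home phase.** From the document: four groups of 27, 16 days, alpha 0.05, Kruskal-Wallis. Assumed, because the document gives no TS rates: a Poisson number of episodes per participant, length 1–3 days, score 1–5. The null has mean 1.2 episodes in every arm. The effect is mean 1.5 in two arms and 0.8 in the other two. Onset is either spread evenly over the 16 days or early (geometric, p = 0.5).

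| Four-group Kruskal-Wallis | Even onset | Early onset |
|---|---|---|
| No effect: at least one of 16 days p < 0.05 | about 45% | about 25% |
| Effect: one day alone | about 12% | about 42% on day 2 |
| Effect: any day, Bonferroni over 16 | about 16% | about 20% |
| Effect: 16-day total | about 66% | about 60% |
| Effect: participant's peak | about 54% | about 53% |

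Under the effect with even onset, at least one uncorrected daily test is below 0.05 in about 80% of trials.

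I repeated these runs with 1,500 trials per scenario. The null figures were 47–48% (even) and 24% (early). The early-onset Bonferroni figure was 20% when a later episode overwrites an earlier one on the same day, and 23% when the higher score is kept. Power for the total was 58–65%. The conclusions do not change.

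**4. A second model.** Here TS is on or off each day at 18 post-baseline times. The assumed daily risk is 20–30% without arginine and 0.6 times that with it. A participant random effect on the logit scale has SD 0 to 1.5.
- One time alone: 12–18% power.
- Any time after Bonferroni over 18: 15–29%.
- Four-group test of the sum over all 18 times: 35–91%.
- Four-group test of the at-home mean: 35–89%.
- No effect (SD 0.5): at least one uncorrected time significant in 57% of trials.
- Very persistent differences between people (SD 2.5): 9% for one time, 8% after Bonferroni, 13% for the sum.

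**The case against.** The strongest case against is that the plan probably does not intend 16 daily tests. The list of evaluation times can be read as four periods, and 0.008 fits exactly four. With one at-home value per participant, much of the problem goes away: in the second model the at-home mean has nearly the same power as the whole-course sum. This is a fair reading, and the 0.008 is the best evidence for it. It does not close the gap, because the text says daily and names no way of forming the single value. Both readings need the same repair.

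Three stronger inferences are tempting, and the document does not support them.
- *TS comes and goes on different days in different people.* The document does not describe the day-to-day pattern. It is an assumption, and the size of the gain rests on it.
- *The plan would miss a real effect.* Uncorrected daily tests flag some day in about 80% of trials under the assumed effect. The main fault is that such a flag cannot be told from chance, since it also appears in about 25–45% of trials with no effect.
- *A peroxide-time effect in particular would be lost.* The peroxide is applied in-office, and the plan already compares arms at one common time immediately afterward. The argument about scattered days does not apply to that test.

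**Conclusion.** The point holds as a gap in specification. For the at-home phase the plan gives no single between-arm TS result. It offers either an uncorrected family of daily tests or an at-home value whose definition is left open.

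Under the assumed episode model, one test of the 16-day total has roughly three to four times the power of Bonferroni-corrected daily tests (60/20 = 3; 66/16 ≈ 4) and keeps its false-positive rate near 5%. All rates, effects and patterns behind these figures are assumptions. The advantage is largest if TS is intermittent, smaller if it clusters early (42% on the best day against 60% for the total), and slight if the same people have TS throughout (9% against 13%). The absence of an overall at-home answer does not depend on any of these inputs.

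**What to change.** In the Statistical Analysis Plan:
1. Reconcile the daily wording with the 0.008 threshold by stating how many TS times enter the analysis.
2. Pre-specify one at-home TS summary per participant as the main between-arm at-home comparison, for example the sum or mean of the daily scores. Name the scale, since two are listed and the document does not say which is recorded daily.
3. State whether the summary is tested across the four groups or by arginine and by peroxide time.
4. Give a missed-day rule, for example the mean of recorded days × 16 if the sum is used.
5. Keep the immediate in-office and 48-hour comparisons as separate named tests.
6. Report the peak score and the proportion with any TS as supporting results, and the day-by-day comparisons as descriptive.

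The cost is SAP wording and one derived variable. If daily scores are recorded as the plan implies, no new data are needed. The downside is that day-level p-values become descriptive and the missed-day rule has to be set before the results are seen.
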